#### **4.6.3 EQ-5D-5L**

The EQ-5D-5L Questionnaire is a health utility measure to assess patients' health status using 5 dimensions. All five dimensions can be combined in a five-digit number which then describes the patient's health state. This descriptive number is converted to a single summary index utility score by using published weights; in this study we use the UK crosswalk value set (as published by the EuroQol Research Foundation at <http://www.euroqol.org/about-eq-5d/valuation-of-eq-5d>).

Additionally, in the second part of the questionnaire, the current health status is measured by the visual analog scale VAS with values ranging from 0 to 100.

The number and percentage of patients who complete the EQ-5D-5L will be summarized at each scheduled time point. The compliance rate (see section 4.6.2) will be plotted over time. For each of the EQ-5D-5L assessments over time, the number and percentage of patients in each of the five categories for each question will be evaluated. A summary of the EQ-5D-5L index utility score at each visit and the associated change from baseline will

also be provided. The summary statistics presented will include the mean, standard deviation, median, minimum, maximum and interquartile range. Corresponding mean (+95% CI) plots are provided.

In addition, summary statistics including mean, standard deviation, median, minimum, and maximum will be calculated according to the patients' health state using the EuroQoL visual analogue scale (EQ-VAS).

The change from baseline to Post-baseline will be analyzed using the paired t-test. The same outputs will be produced for the EQ-5D-5L VAS score.

The proportion of patients who report changes that exceed the clinically meaningful threshold on the EQ-5D-5L index and the EQ-VAS scores will be reported. A clinically meaningful improvement threshold is defined as a change of +0.07 points in the index utility score and +7 points in the VAS score.

For all completed assessments the five dimensions, the index utility score and VAS score is displayed in a separate listing.

#### **4.6.4 Patient preference**

Summary statistics on patient preference for the emicizumab regimen compared with the previous regimen used will be presented.

Preference survey, which is administered to patients at Month 3, consists in main questions:

- the first question is related to the treatment preference with 3 possible responses: (a) older hemophilia IV treatment prior to enrollment in the study; (b) new study drug SC emicizumab treatment; (c) no treatment preference.
- the second question, only asked to patients with a preference (responses a or b at first question), is related to factors influencing treatment preference (14 possible factors). For each factor, the patient should tick whether the factor is important and, if yes, provide an importance rank for the top 3 factors ("1" being the most important, "2" the second most important and "3" the third most important)

The number and percentage of patients who complete the Preference survey will be summarized.

Proportion of patients preferring the older hemophilia treatment, emicizumab, or without treatment preference will be computed along with 95% CIs (using the Pearson–Clopper one sample binomial method).

This defines two sub-populations of the "All patient population":

- The PREFSC population, which includes all the patients that responded: "Prefer the new study treatment (SC)"
- The PREFIV population, which includes all the patients that responded: "Prefer my old hemophilia treatment (IV)"

For patients who have a preference to either emicizumab or the old IV hemophilia treatment, the factors influencing the preference can be treated like ordered categorical variables as follow:

- Category 1 = “Most important”, when factor was ranked first among top factors
- Category 2 = “2nd most important”, when factor was ranked second among top factors
- Category 3 = “3rd most important”, when factor was ranked third among top factors
- Category 4 = “Influenced preference but not most important”, when factor was ticked but not ranked among top factors
- Category 5 = “Did not influence preference”, when factor was not ticked as important

Summaries of these categories will be produced by factor for the PREFSC and the PREFIV populations. Bar charts showing proportions of patient within each preference factors will also be produced for the PREFSC and the PREFIV populations:

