**If you indicated a preference, please complete question 2.**

**If you did not have a preference, you do not need to complete questions 2.**

## Appendix 3 EmiPref Patient Preference Questionnaire (cont.)

2. Below are some factors that may have influenced your treatment preference. Please indicate which factors had an influence on YOUR preference. Please indicate YES (this influenced my preference) or NO (this did not influence my preference) for each item.

On those you said YES to, please rank the top 3 in order of importance (1 being the “most important” reason for your preference).

	Yes	No	Importance rank
Route of administration (IV or SC) was easier			
Pain associated with treatment was less			
Worry about finding a vein was less			
Concern over port use/infection was less			
Administration was easier			
Able to keep treatment at room temperature			
Time to administer treatment was shorter			
The frequency of treatments was lower			
Effect on other activities (work, school, sports, social interactions) was less			
Impact on family members and friends was less			
Worries about having a bleed were less			
Quality of life, in general, was better			
It was easier to take every dose my doctor recommended			
Made me feel more ‘normal’			

3. Please add any additional information about your experience with the study drug (SC emicizumab).

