#### **2.2.5 Treatment Preference Questionnaire**

Patient preference will be assessed through a paper version of the EmiPref questionnaire (see Protocol Appendix 3), which asks patients to specify the treatment they would prefer to continue to receive after receiving treatment with their previous episodic or prophylactic regimen and SC emicizumab. Patients who express a preference are then asked to identify the reasons which may have influenced their decision and indicate the top three reasons for their choice. Patients will complete this questionnaire after 3 months of treatment with emicizumab.

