## **4. STATISTICAL METHODS**

No formal statistical hypothesis tests will be performed and all analyses are considered descriptive.

Categorical data will be summarized using frequencies and percentages (including a category for missing, if appropriate). Continuous data will be summarized using descriptive statistics (N, mean, standard deviation, median, lower quartile, upper quartile, minimum and maximum). Other analysis methods will be specified (below) where applicable.

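### SAP 4.6.4 does not separate an explicit NO from an unanswered item on the paper EmiPref form, so blanks may be counted as factors that did not influence preference

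*SAP*

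**What the plan says.** SAP 2.2.5 sets the mode of collection: "Patient preference will be assessed through a paper version of the EmiPref questionnaire". Question 2 goes only to patients who prefer one of the two treatments.

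SAP 4.6.4 describes the response as a single mark: "For each factor, the patient should tick whether the factor is important", with a rank for the top three. It then defines ordered categories for each factor:

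- Category 1 applies "when factor was ranked first among top factors"; Categories 2 and 3 are the same for ranks two and three.
- Category 4 applies "when factor was ticked but not ranked among top factors".
- Category 5 (no influence) applies "when factor was not ticked as important".

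These categories are tabulated by factor and shown as bar charts, separately for patients preferring emicizumab (PREFSC) and patients preferring their old IV treatment (PREFIV).

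The form in Protocol Appendix 3 works differently. Its instruction is: "Please indicate YES (this influenced my preference) or NO (this did not influence my preference) for each item". It has Yes, No and rank columns, and asks for ranks only among the factors marked YES.

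On missing values, SAP section 4 has a general provision: "Categorical data will be summarized using frequencies and percentages (including a category for missing, if appropriate". SAP 4.11 lists imputation rules for bleed and treatment data and none for EmiPref. SAP 4.6.4 summarises completion per patient, not per item.

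**The concern.** On this form NO is a positive answer and an empty line is no answer. The Category 5 wording treats the form as a tick list, on which the two look the same. A patient who states a preference and leaves question 2 empty would contribute 14 entries saying that a factor had no influence.

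Such blanks are possible. SAP Appendix 3 says that patients cannot skip items on the electronic quality-of-life questionnaires; nothing comparable is described for the paper EmiPref. Elsewhere the SAP keeps non-answers apart from answers: missing adverse event severity is classed as unknown (4.9.2), and not-applicable responses on the quality-of-life scales are recoded as missing (Appendix 3).

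At stake is the accuracy of the tables of reasons. Protocol 3.3.10 wants the survey to explore why patients prefer a treatment, and these tables are the planned output for that. Two programmers working from the same SAP could also code the same form differently.

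**Working it through.** The plan states no figure on this point, so there is none to reproduce. The check compares the texts and then works out the size of the effect.

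**How each response pattern is classified**

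| Marks on the form | SAP 4.6.4, read literally | Meaning on the form |
|---|---|---|
| YES and a rank of 1 to 3 | Category 1, 2 or 3 | A top reason |
| YES, no rank | Category 4 | A reason |
| NO | Category 5 | Not a reason |
| No box, no rank | Category 5 | Not answered |
| No box, rank of 1 to 3 | Category 1 to 3 by rank; also meets Category 5 | Probably YES, since ranks are asked only for YES items |

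The fourth row is the main problem. The fifth is a small overlap for which no precedence is stated.

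**Size**

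For one factor, let

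- p = share influenced (YES or ranked) among patients who answered the item;
- b = share of patients who left it blank and unranked;
- q = share of those blanks that would have been YES.

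None of these is given in the documents. The values below are assumptions.

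- Share reported under the literal rule: (1 − b)p
- Share if everyone had answered: (1 − b)p + bq
- Error of the literal rule: −bq
- Error of an answered-only share: p − [(1 − b)p + bq] = b(p − q)

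With p = 60%:

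| b | Literal rule reports | Understated if blanks resemble answers (q = 60%) | Largest understatement (q = 100%) | Answered-only overstates if blanks mean NO (q = 0) |
|---|---|---|---|---|
| 0% | 60.0% | 0 | 0 | 0 |
| 2% | 58.8% | 1.2 points | 2.0 points | 1.2 points |
| 5% | 57.0% | 3.0 points | 5.0 points | 3.0 points |
| 10% | 54.0% | 6.0 points | 10.0 points | 6.0 points |
| 20% | 48.0% | 12.0 points | 20.0 points | 12.0 points |

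At b = 10% with blanks resembling answers, the understatement is 0.10 × 30% = 3.0 points when p = 30% and 0.10 × 90% = 9.0 points when p = 90%.

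With blanks shown separately, the reader can bound the full-response value between (1 − b)p and (1 − b)p + b. For p = 60% and b = 10% this is 54.0% to 64.0%.

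In a small group one form matters. If PREFIV held 5 patients (assumed), one empty question 2 could turn 4/4 into 4/5 for a factor, a change of 20 points.

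**The case against.** The best defence is that the SAP already describes a yes/no response. It asks whether the factor is important and, if so, for a rank, so not being ticked as important may be shorthand for the NO box. The general missing category in SAP section 4 could then take the blanks. Protocol 4.5.9 also expects questionnaires to be completed in full, and Protocol 6.5 plans a summary of adherence with the preference measure.

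This stands in part: it is not certain that blanks would be coded as NO. But the five definitions as worded leave no item unclassified, so nothing remains for a missing category to hold, and 4.6.4 does not invoke one. An expectation of full completion does not prevent blanks on paper, and the completion summary in 4.6.4 does not show which items were skipped.

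A second objection concerns the remedy, and it stands. If patients mark only the factors that apply, blanks mean NO. The literal rule is then unbiased and an answered-only share overstates.

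Third, the overlap of a ranked factor with Category 5 matters little, because the form asks for ranks only on YES items and Categories 1 to 3 depend on rank alone.

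Some stronger readings are tempting but unsupported:

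- A reader might infer that every reason is understated. That would require each factor to have blank, unranked items, some of which would have been YES.
- A reader might take the reasons to be part of the secondary endpoint. The endpoint in Protocol section 2 is the preference itself, which comes from question 1.
- A reader might suppose that later items on the list are skipped more often, distorting the comparison of factors. Nothing in the documents says so.

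**Conclusion.** The point holds as a minor defect in the definition of Category 5. Followed literally, SAP 4.6.4 codes a blank and unranked item as NO on a form that offers NO as a separate answer, and no other rule clearly overrides this. A factor's share influenced can be understated by up to its share of blank items. The understatement is zero if there are no blanks or if every blank stands for NO. The sizes worked out above rest on assumed blank rates, response shares and group size.

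The effect is confined to the descriptive tables and bar charts of reasons in PREFSC and PREFIV. The proportions preferring each treatment, with their exact confidence intervals, do not use question 2. The primary safety analysis and the sample size are not affected.

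**What to change.** In SAP 4.6.4:

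- assign Category 5 only when NO is ticked;
- count a ranked factor with no box ticked under its rank;
- classify a factor with no box ticked and no rank as missing, and report the number missing per factor;
- show the share influenced twice: among patients who answered the item, and among all patients in the group with blanks taken as NO.

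Both denominators are needed because neither is right in every case. The answered-only share is too high if blanks mean NO, and the all-patient share is too low if some blanks would have been YES. The missing count also lets a reader work out the upper bound, with every blank taken as YES.

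The cost is a wording change, one added row per factor, the second share, and denominators that differ slightly between factors. No new data are needed.

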#### **4.6.5 Exploratory Efficacy Endpoints**

Analysis on 12- and 24-week interval:

Additional analysis of the calculated ABR and the number of patients with zero bleeds will be performed for 12- and 24-week intervals on treated bleeds, all bleeds, treated spontaneous bleed, treated joint bleeds and treated target joint bleeds. The 12/24-week intervals are based on the start and end of the Efficacy Period. A patient has only as many 12/24-week intervals as fully fit into this period. E.g. if the duration of Efficacy Period is 98 days (=14 weeks) he has one full 12-week interval and no full 24-week interval. A bleed is assigned to a certain 12/24-week interval based on the distance between bleed date and start of efficacy period. If a bleed is after the end of the last full interval it is not taken into account.

The calculated ABR for a 12/24-week interval will be derived using the following formula which is based on the general formula:

$$\frac{\text{Number of bleeds during the 12 or 24 – week interval}}{84 \text{ or } 168 \text{ days}} \times 365.25$$

The calculated ABRs will be summarized and a graph for the 12- and 24-week intervals for all subjects will be provided. The table will include the mean with the 95% CI based on Exact Poisson, the median with the IQR and the minimum and maximum.

The number of subjects with zero bleeds within a 12- or 24-week interval will be summarized separately and a graph for all subjects will be provided. The table will include the number and percentage of the subjects with zero bleeds and the 95% CI using the Clopper-Pearson method.

The same analysis as described above may also be performed on 36-, 48-, 60- and 72- and 98-week interval if sufficient number of patients available.

#### **4.6.6 Sensitivity Analyses**

The sensitivity analyses will include different methods to define bleeds or eligible bleed data and different statistical models and will be applied to all efficacy endpoints defined in section 4.6.1.1.

Different ways to define bleeds or eligible bleed data:

- Include all bleeds recorded: without the 72-hour rule and “treated bleeds” but excluding bleed due to surgery and procedure
- Include only patients who received at least 12 weeks of emicizumab treatment, i.e. efficacy period  $\geq 12$  weeks
- Include only the first 24 weeks of efficacy period in the analysis. The calculated ABR is based on Bleeds that occurred before or on day 168 from efficacy period start. Withdrawals are included for the time they were followed for. The 24 weeks Efficacy Period ends 168 days after efficacy period start, the Cut-off date, the date of withdrawal or the end date of efficacy period 1, whichever comes first.

#### **4.6.7 Subgroup Analyses**

Descriptive summaries of both treated bleeds and all bleeds will be produced on the subgroups presented below. The summaries will include subgroup model based ABR (95% CI) and calculated mean ABR (95% CI).

The pre-specified subgroups are:

- Age at baseline:  $< 18, \geq 18$
- Age at baseline:  $< 65, \geq 65$
- Race: Asian, Black or African American, White, Other
- Number of bleeds during 24 weeks prior to study entry:  $< 9, \geq 9$
- Number of target joints at baseline: no target joint, any target joint
- Hemophilia severity: mild, moderate, severe
- Previous treatment regimen: prior episodic, prior prophylactic (in case a subject have history of both prior episodic and prior prophylactic treatments, he will be considered as prophylactic)

Additional region- and/or country-specific analyses may be performed to support regulatory submission as needed.

#### **4.6.8 Number of Days Hospitalized**

The number of days of hospitalization, during the efficacy period, will be summarized.

### **4.7 PHARMACOKINETIC AND PHARMACODYNAMIC ANALYSES**

PK analyses will be provided by clinical pharmacology.

For all patients, pre-dose (concentration at the end of the dosage interval [ $C_{\text{trough}}$ ]) plasma concentrations of emicizumab will be presented descriptively for each timepoint. Data presented will include arithmetic and geometric means, median, range, standard deviations, and coefficients of variation.

## 4.8 IMMUNOGENICITY ANALYSES

The immunogenicity analyses will include patients with at least one pre-dose and one post-dose anti-emicizumab antibody assessment. Immunogenicity summary tables will be restricted to the period before up-titration, if any, except if stated otherwise.

Patients treated with emicizumab may develop anti-therapeutic antibodies (ATA).

The proportion of all ATA positive patients will be summarized by visit and overall. The by visit summary includes positive/negative status directly from the data. For the overall summary the status is derived as described below.

Overall ATA positivity/negativity to be reported in 4 categories:

- **NEGATIVE**
  - ✓ patient negative at baseline and negative after treatment start
  
- **NEGATIVE (TREATMENT UNAFFECTED)**
  - ✓ patient positive at baseline and negative after treatment start
  - ✓ treatment unaffected (negativity after baseline) defined as a maximum post-baseline titer lower than patient's baseline titer multiplied by 4
  
- **POSITIVE (TREATMENT BOOSTED)**
  - ✓ patient positive at baseline and positive after treatment start
  - ✓ treatment boosting (positivity after baseline) defined as a maximum post-baseline titer increase greater or equal to patient's baseline titer multiplied by 4
  
- **POSITIVE (TREATMENT INDUCED)**
  - ✓ patient negative at baseline and positive after treatment start

A patient is considered positive if a titer value  $> 0$  is reported. As soon as a patient fulfills the criteria of positivity at one post baseline time point, the patient is counted as positive, i.e., a negative patient has a negative result at all timepoints.

The relationship between ATA (anti-emicizumab antibodies) and safety, efficacy, and/or PK may be analyzed and reported descriptively via subgroup analyses.

**Note:** The summaries will be provided separately for up-titrated patients and the overall status is defined separately by dose. The baseline is the original baseline and not the baseline just before up-titration.

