## **6.6 IMMUNOGENICITY ANALYSES**

Data on the impact of immunogenicity (anti-emicizumab antibodies) on safety, efficacy, and/or PK will be summarized using standard language/terminology ([Shankar et al. 2014](#)).

The immunogenicity analyses will include patients with at least one pre-dose and one post-dose anti-emicizumab antibody assessment. The numbers and proportions of antibody-positive patients and antibody-negative patients during the treatment period will be summarized. Patients are considered to be antibody-positive if they are negative at baseline but develop an anti-emicizumab antibody response following *emicizumab* administration (treatment-induced antibody response), or if they are positive at baseline and the titer of one or more post-baseline samples is at least 4-fold greater (i.e.,  $\geq 0.60$  titer units) than the titer of the baseline sample (treatment-enhanced antibody response). Patients are considered to be antibody-negative if they are negative at baseline and all post-baseline samples are negative, or if they are positive at baseline but do not have any post-baseline samples with a titer that is at least 4-fold greater than the titer of the baseline sample (treatment unaffected). The relationship between anti-emicizumab antibody status and safety, efficacy, and PK endpoints will be analyzed and reported descriptively via subgroup analyses.

A detailed description of the statistical methods that will be used for the secondary analyses will be provided in the SAP.

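### SAP 4.8 does not reproduce the protocol's 4-fold rule for treatment-boosted antibodies, and its boosted and unaffected categories are not complements

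*SAP*

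**What the plan says.** Protocol 6.6 counts a baseline-positive patient as antibody-positive (treatment-enhanced) when the "titer of one or more post-baseline samples is at least 4-fold greater" than the baseline titer, and gives the same cut-off as at least 0.60 titer units. Baseline-positive patients who "do not have any post-baseline samples with a titer that is at least 4-fold greater than the titer of the baseline sample" are antibody-negative (treatment unaffected). There is one threshold, and the two classes are exact complements.

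SAP 4.8 reports overall status in four categories. For baseline-positive patients it has two:

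- NEGATIVE (TREATMENT UNAFFECTED): "defined as a maximum post-baseline titer lower than patient's baseline titer multiplied by 4".
- POSITIVE (TREATMENT BOOSTED): "defined as a maximum post-baseline titer increase greater or equal to patient's baseline titer multiplied by 4".

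SAP 4.8 does not mention 0.60 titer units and does not say whether titers are raw or logarithmic. After the categories it says that a titer above zero is positive, then: "As soon as a patient fulfills the criteria of positivity at one post baseline time point, the patient is counted as positive". It concludes that "a negative patient has a negative result at all timepoints".

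The SAP history records that the definition of positive patients was updated in version 3.0 for consistency with two other emicizumab studies. It does not reconcile the change with Protocol 6.6.

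**The concern.** The protocol's immunogenicity endpoint is the incidence and clinical significance of anti-emicizumab antibodies. For a patient already positive at baseline, the boosted or unaffected call decides whether that patient adds to the incidence. SAP 4.8 also allows this status to define subgroups for safety, efficacy and PK.

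The two SAP conditions use different quantities. One compares the titer reached with 4 times baseline; the other compares the increase in titer with 4 times baseline. On a log scale, moreover, a fold change is an added constant, so multiplying the baseline value by 4 is not a 4-fold rule. Two programmers following the text could therefore produce different tables, and neither need match the protocol.

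**Working it through.** **Inputs.** From Protocol 6.6: ratio 4, or 0.60 titer units. From SAP 4.8: unaffected if maximum post-baseline titer < 4b; boosted if maximum increase ≥ 4b, where b is the baseline titer.

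**Step 1: the protocol's own equivalence.** log10(4) = 0.602, and 10^0.60 = 3.98, so 4-fold and 0.60 agree on a log10 scale. They do not agree on the other usual scales: ln(4) = 1.386 and log2(4) = 2. The protocol's titer units are therefore log10 titers. The figure also settles that the protocol means a ratio of 4, not 5, since log10(5) = 0.699.

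**Step 2: raw titers.**

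- Protocol boosted: post ≥ 4b.
- SAP unaffected: post < 4b.
- SAP boosted, read literally: post − b ≥ 4b, that is, post ≥ 5b.

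Titers in [4b, 5b) meet neither SAP condition. For b = 10 the gap is 40 to below 50; for b = 100 it is 400 to below 500. A titer of exactly 4 times baseline, the protocol's boundary case, falls in the gap. If increase is read loosely as the titer reached, the SAP condition becomes post ≥ 4b, which is the protocol's rule with no gap.

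**Step 3: log10 titers.** The protocol condition becomes post ≥ b + 0.60. The SAP conditions, applied to the reported value, stay at < 4b (unaffected) and ≥ 5b (boosted, literal) or ≥ 4b (boosted, loose).

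| b | Protocol boosted from | SAP unaffected below | SAP boosted from (literal) | Boosted per protocol, NEGATIVE per SAP |
|---|---|---|---|---|
| 0.10 | 0.70 | 0.40 | 0.50 | none |
| 0.20 | 0.80 | 0.80 | 1.00 | none |
| 0.60 | 1.20 | 2.40 | 3.00 | 1.20 to < 2.40 |
| 1.00 | 1.60 | 4.00 | 5.00 | 1.60 to < 4.00 |

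The rules cross where b + 0.60 = 4b, so b = 0.60/3 = 0.20 (loose), and where b + 0.60 = 5b, so b = 0.60/4 = 0.15 (literal). Above 0.20 there is always a range that the protocol calls boosted and the SAP calls negative. At b = 1.0 that range runs from 4-fold to just under 10^(4.00 − 1.00) = 1,000-fold, and titers from 4.00 to below 5.00 have no category on the literal reading. Below the crossing the error reverses: at b = 0.10 the SAP calls a rise of 10^0.30 = 2.0-fold (loose) or 10^0.40 = 2.5-fold (literal) boosted.

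**Step 4: the closing sentences.** Take a baseline-positive patient whose titer does not change. The maximum titer is b, which on raw titers is below 4b, so the category is NEGATIVE (TREATMENT UNAFFECTED). Yet each of this patient's titers is above zero and so positive, and the baseline sample is positive by definition. The patient cannot have a negative result at all timepoints. A log10 scale does not remove the conflict: with any titer above zero, an unchanged titer is still below 4 times itself.

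**Step 5: size.** The documents give no proportion of baseline-positive patients. Assuming 1% to 5% of about 200 gives 200 × 0.01 = 2 to 200 × 0.05 = 10 patients.

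**The case against.** The strongest reply is that the SAP intends the protocol's rule and words it loosely. The unaffected condition on raw titers is exactly the protocol's complement. Both categories name the same 4-times-baseline quantity, which suggests a single threshold, and a rule that any titer above zero is positive reads naturally as a raw-titer rule. On raw titers with increase read as the level reached, SAP and protocol agree. This stands as a possible intention. It requires setting aside the word increase and assuming a scale that the SAP does not state and that does not fit the protocol's 0.60.

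It can also be said that the closing sentences do not contradict the categories. SAP 4.8 separates by-visit status, taken directly from the data, from derived overall status, and the criteria of positivity may mean the boosted criteria. That reading can rescue the sentence about one positive time point. It does not rescue the statement about negative results at all timepoints, because an unaffected patient was positive at baseline.

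The practical effect is limited. All analyses are descriptive, patients who received emicizumab in a prior investigational study are excluded, and unaffected patients have their own row and a by-visit summary, so they are not hidden among true negatives. Protocol 1.2.2.5 reports no positives among 171 patients in HAVEN 1 and 2, and 4 among 18 in the dose-finding trial. Those are any-time positives, not baseline positives, so they do not size the group affected here.

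**Conclusion.** The discrepancy is real. Read literally, SAP 4.8 does not give the protocol's classification on either scale: on raw titers it leaves 4 to under 5 times baseline unclassified, and on log10 titers it moves the cut-off by an amount that depends on baseline.

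A reader might infer that the gap causes boosted patients to be reported as negative. It does not: a titer in [4b, 5b) is not below 4b, so it cannot enter the unaffected category and is left without one. Reporting boosted patients as negative follows only if the factor 4 is applied to log10 titers with baseline above about 0.20. The protocol's figure implies that scale, but the SAP does not confirm it. For the same reason, it should not be said that the SAP demands a rise of 1,000-fold, or of 10^(5.00 − 1.00) = 10,000-fold on the literal reading. Those values belong to one assumed scale and one baseline, 1.0. Nor does the error run only towards under-calling, since it reverses at very low baselines.

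Only baseline-positive patients are affected. Under the assumed 1% to 5% they number 2 to 10, and only those whose rise falls in a disputed range would change category. The effect on the overall table is probably small, but the text should be settled before it is programmed.

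**What to change.** In SAP 4.8:

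1. State the scale on which titers are reported, including for the above-zero cut-off.
2. Define BOOSTED as maximum post-baseline titer ≥ 4 × baseline (raw) or ≥ baseline + 0.60 (log10), using the line that matches the stated scale.
3. Define UNAFFECTED as the exact complement among baseline-positive patients.
4. Keep a titer above zero as the sample-level rule for positivity, including at baseline. It is the section's only rule for identifying baseline-positive patients, so it should not be restricted to baseline-negative ones.
5. In the overall status, apply the two patient-level sentences (one positive post-baseline result makes the patient positive; a negative patient is negative throughout) to baseline-negative patients only.

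With these definitions the gap is zero. For a baseline of 1:10, every later titer of 1:40 or more (log10 ≥ 1.60) is boosted and every lower one is unaffected. The cost is a few lines of SAP text and one derivation line, with no new data collection.
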